## 9.3. Variables

### 9.3.1. Outcomes

The primary outcomes of interest will be (see Table 3 for operational definitions):

- The demographics, comorbidities, and prior and current medications (including prior use of biologics) of tofacitinib patients;d,e
- Prescribers' adherence to the tofacitinib aRMMs, specifically:
  - Compliance to the recommended posology per indication and duration of use, as measured by:f
    - ADD of tofacitinib therapy, calculated in 8-week intervals from Week 0 through Week 47, and reported in the following categories:
      - Up to 5 mg ADD;
      - >5 to 11 mg ADD;

<sup>c This exclusion criterion will primarily apply to those patients who received their index tofacitinib prescription for an indication within the first 3 months after approval of that indication.

<sup>d The data sources are unable to reliably ascertain severity of hepatic impairment and renal impairment.

<sup>e In GKV claims, outpatient diagnoses are reported quarterly.

<sup>f The study outcomes that contain an ADD component will *not* be assessed in Hungary or the Netherlands. The Hungarian administrative claims database is unable to estimate ADD, either directly or by proxy, due to how tofacitinib is captured in the database. In the high-budget impact medication dataset of the PHARMO Database Network (Netherlands), neither ADD nor the number of pills per prescription is captured.

- >11 to 15 mg ADD;
- >15 to 20 mg ADD; and
- >20 mg ADD;

Note that within these reporting intervals and categories, ADD will also be reported by approved indication or by the indication groups: "PsA or RA" and "UC", presence of  $\geq$ 1 VTE risk factor prior to tofacitinib initiation, and prior use of an alternative therapy (i.e., biologic) in the 12 months prior to tofacitinib initiation; depending on the objective, outcomes will be stratified by reporting period;e,g

- The proportion of patients with an ADD of >11 mg during any of the 8-week follow-up intervals and no evidence of a diagnosis for UC; and
- The proportion of patients with an ADD of ≥15 mg in Weeks 16-23, Weeks 24-31, Weeks 32-39, and/or Weeks 40-47 of follow-up with evidence of a diagnosis for UC but no use of an alternative therapy (i.e., biologic) *prior to* tofacitinib initiation;

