Average daily dose (ADD) t	Outcome: Compliance to recommended posology	Defined in Section 9.3.4. Assessed during the follow-up period.	
A patient with an ADD of >11 mg during any of the 8-week follow-up intervals and no evidence of a diagnosis for UC t	Outcome: Compliance to recommended posology	Defined as 0 ICD-10 diagnosis codes for UC prior to and including the date of the first tofacitinib prescription dispensing in an 8-week follow-up interval that has an ADD of >11 mg (ADD defined in Section 9.3.4).	

1 able 5. Operational definitions of study variables in the selected databas	Table 3.	Operational definitions of stud	y variables in	the selected	database
--	----------	--	----------------	--------------	----------

<sup>s In GKV claims, outpatient diagnoses are reported quarterly.

<sup>t The study outcomes that contain an ADD component will *not* be assessed in Hungary or the Netherlands. The Hungarian administrative claims database is unable to estimate ADD, either directly or by proxy, due to how tofacitinib is captured in the database. In the high-budget impact medication dataset of the PHARMO Database Network, neither ADD nor the number of pills per prescription is captured.

Variable	Role	Operational definition	
A patient with an ADD of $\geq$ 15 mg in Weeks 16-23, Weeks 24-31, Weeks 32- 39, and/or Weeks 40-47 of follow-up with evidence of a diagnosis for UC but no use of an alternative therapy (i.e., biologic) prior to tofacitinib initiation t	Outcome: Compliance to recommended posology	Defined as ≥1 ICD-10 diagnosis codes for UC and ≥1 prescription dispensing for a biologic (as identified by ATC codes) prior to and including the date of the index tofacitinib prescription with an ADD ≥15 mg in Weeks 16-23, Weeks 24-31, Weeks 32-39, and/or Weeks 40- 47 of follow-up (ADD defined in Section 9.3.4). Complete list of biologics in ANNEX 6. LIST OF ATC CODES FOR MEDICATIONS OF INTEREST TO AVOID WHILE TAKING TOFACITINIB. Note: This definition will miss those who have 1 10-mg BID prescription and the remaining prescriptions are 5-mg BID.	
Compliance to patient screening and laboratory monitoring prior to and during tofacitinib treatment u			

 Table 3.
 Operational definitions of study variables in the selected databases

The following recommended screenings and monitoring will be assessed in the following timeframes:

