History of malignancy (non-metastatic and metastatic; excluding non- melanoma skin cancer)	Outcome: VTE risk factor	Defined as ≥1 ICD-10 diagnosis code for malignancy (excluding non-melanoma skin cancer) in the 12 months prior to or on the day of the index tofacitinib dispensing.
Age >50 years at tofacitinib initiation	Outcome: VTE risk factor	Defined as age at tofacitinib initiation >50 years.
History of diabetes	Outcome: VTE risk factor	Defined as $\geq 1$ ICD-10 diagnosis code for diabetes in the 12 months prior to or on the day of the index tofacitinib dispensing.
History of hypertension	Outcome: VTE risk factor	Defined as ≥1 ICD-10 diagnosis code for hypertension in the 12 months prior to or on the day of the index tofacitinib dispensing.
Initiating tofacitinib with ≥1 VTE risk factor	Outcome: VTE risk factor	Defined as ≥1 VTE risk factor (as listed and defined above) identified in the 12 months prior to or on the day of the index tofacitinib dispensing (unless otherwise specified).
Number of VTE risk factors identified prior to tofacitinib initiation	Outcome: VTE risk factor	Calculated as the sum of the number of VTE risk factors (as listed and defined above) identified in the 12 months prior to or on the day of the index tofacitinib dispensing (unless otherwise specified).

Table 3.	Operational	definitions of	f study	variables in	the selected	databases
----------	-------------	----------------	---------	--------------	--------------	-----------

Variable	Role	Operational definition
Number of UC patients with: ≥1 VTE risk factor; no prior alternative therapy (i.e., biologic); and an ADD >10 mg in Weeks 16-23, Weeks 24- 31, Weeks 32-39, and Weeks 40-47 of follow-up t	Outcome: VTE risk factor	Defined as a patient meeting all of the following criteria: ≥1 ICD-10 diagnosis code for UC; ≥1 VTE risk factor (as listed and defined above); 0 prescription medication dispensings for a biologic (as identified by ATC codes) in the 12 months prior to and including the date of the index tofacitinib prescription dispensing; and an ADD of >10 mg in Weeks 16-23, Weeks 24-31, Weeks 32- 39, and Weeks 40-47 of follow-up, respectively (ADD defined in Section 9.3.4). Complete list of biologics in ANNEX 6. LIST OF ATC CODES FOR MEDICATIONS OF INTEREST TO AVOID WHILE TAKING TOFACITINIB.

 Table 3.
 Operational definitions of study variables in the selected databases

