Continuation of tofacitinib after developing ≥1 VTE risk factors while taking tofacitinib	Outcome: VTE risk factor	Defined as $\geq 1$ VTE risk factor while receiving tofacitinib therapy (as listed and defined above) PLUS $\geq 1$ prescription dispensing for tofacitinib within a specific time window after the code for the VTE risk factor.
		Note: The time window for when to look for a tofacitinib prescription dispensing will be specific to the VTE risk factor acquired while receiving tofacitinib therapy and will be operationalized during SAP development.
		Duration of tofacitinib therapy defined in Section 9.3.3.
Compliance to recommend	lations for limitations of use in patie	nts aged 65 years and older
Initiating tofacitinib with no prior use of an alternative therapy (i.e., biologic) among patients 65 years of age and older	Outcome: Age 65 years and older	Defined as patients who are 65 years and older on the date of the index tofacitinib dispensing with 0 prescription dispensings for a biologic (as identified by ATC codes) in the 12 months prior.
		Complete list of biologics in ANNEX 6. LIST OF ATC CODES FOR MEDICATIONS OF INTEREST TO AVOID WHILE TAKING TOFACITINIB.

Table 3.	Operational	definitions of	fstudy	variables in	the selected	databases
----------	-------------	----------------	--------	--------------	--------------	-----------

Variable	Role	Operational definition
Discontinuation of tofacitinib for patients who turn 65 years old while receiving tofacitinib	Outcome: Age 65 years and older	Defined as patients aged 65 years, receiving tofacitinib, who have 0 prescription dispensings of tofacitinib from the time they turn 65.5 years old through to the end of the follow-up period.
		Note: Patients have 6 months to discontinue tofacitinib to allow them time to be seen by their healthcare provider.
		Duration of tofacitinib therapy defined in Section 9.3.3.
Inappropriate continuation of tofacitinib for patients who turn 65 years old while receiving tofacitinib	Outcome: Age 65 years and older	Defined as patients aged 65 years, receiving tofacitinib, who have $\geq 1$ prescription dispensing of tofacitinib from the time they turn 65.5 years old through to the end of the follow-up period and 0 prescription dispensings for a biologic (as identified by ATC codes) prior to that tofacitinib prescription dispensing.

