Initiating tofacitinib with ≥1 CV risk factor and no prior use of an alternative therapy (i.e., biologic)	Outcome: CV risk factor	
 
Defined as ≥1 CV risk factor (as listed and defined above) identified in the 12 months prior to or on the day of the index tofacitinib dispensing—AND—0 prescription medication dispensings for a biologic (as identified by ATC code) in the 12 months prior to and including the date of the index tofacitinib prescription dispensing.
 
Complete list of biologics in ANNEX 6. LIST OF ATC CODES FOR MEDICATIONS OF INTEREST TO AVOID WHILE TAKING TOFACITINIB.
 

 Table 3.
 Operational definitions of study variables in the selected databases

Assessment of CV risk factors while receiving tofacitinib therapy (duration of tofacitinib therapy defined in Section 9.3.3) (will be stratified by sex as outlined in Section 9.7.1.2.2.1.3 [Patients with CV risk factors])

Elderly (patients 65 years and older)	Outcome: CV risk factor	Defined as patients aged 65 years or older while receiving tofacitinib.
Current smoker x	Outcome: CV risk factor	Defined as $\geq 1$ ICD-10 diagnosis code for tobacco use disorder or $\geq 1$ procedure code for counselling visits for smoking or $\geq 1$ prescription dispensing (as identified by ATC code[s]) for a nicotine replacement product while receiving tofacitinib.
Diabetes	Outcome: CV risk factor	Defined as ≥1 ICD-10 diagnosis code for diabetes while receiving tofacitinib therapy.
Hypertension	Outcome: CV risk factor	Defined as ≥1 ICD-10 diagnosis code for hypertension or ≥1 prescription dispensing (as identified by ATC code[s]) for an antihypertensive while receiving tofacitinib. Complete list in ANNEX 8. LIST OF ATC CODES FOR
		ANTIHYPERTENSIVES.
Hyperlipidaemia	Outcome: CV risk factor	Defined as $\geq 1$ ICD-10 diagnosis code for hyperlipidaemia or $\geq 1$ prescription dispensing (as identified by ATC code[s]) for a statin or other antihyperlipidaemic while receiving tofacitinib.
		Complete list in ANNEX 9. LIST OF ATC CODES FOR ANTIHYPERLIPIDAEMICS.

Variable	Role	Operational definition
Coronary artery disease (defined as MI, stroke, CABG [coronary artery bypass graft], or PCI [percutaneous coronary intervention])	Outcome: CV risk factor	Defined as ≥1 ICD-10 diagnosis code for MI or stroke or ≥1 procedure code for CABG or PCI while receiving tofacitinib therapy.

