# 9.7.1.2. Primary Objective 2: Prescribers' adherence to the tofacitinib aRMMsoo,pp

# 9.7.1.2.1. Compliance to the recommended posology per indication and duration of use

Average daily dose, as listed in Table 3 and defined in Section 9.3.4, will be reported for each of the pre-specified time intervals as a continuous and categorical variable and stratified by approved indication group ("RA and PsA" or "UC"), age (e.g., <65 and  $\geq$ 65 years), presence of  $\geq$ 1 VTE risk factor in the 12 months prior to tofacitinib initiation, prior use of an alternative therapy (i.e., biologic) in the 12 months prior to tofacitinib initiation; and reporting period;qq it may additionally be stratified by sex.

Duration of tofacitinib therapy, as listed in Table 3 and defined in Section 9.3.3, will also be described, tabulated, and stratified by age (e.g., <65 and  $\geq 65$  years); it may additionally be stratified by sex.

The variables listed under 'Outcome: Compliance to recommended posology' in Table 3 will be described and tabulated.

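### The Table 3 definition of the UC high-dose outcome requires a prior biologic, although the outcome is defined by having had none

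*Protocol*

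**What the plan says.** Section 9.3.1 lists, among the posology outcomes of primary objective 2, the proportion of patients with ADD of at least 15 mg in Weeks 16-23, 24-31, 32-39 and/or 40-47 "with evidence of a diagnosis for UC but no use of an alternative therapy (i.e., biologic") before starting tofacitinib. The variable column of Table 3 (Section 9.3.2) repeats the condition: "of follow-up with evidence of a diagnosis for UC but no use of an alternative therapy (i.e., biologic) prior to tofacitinib initiation".

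The operational definition beside that name reads differently. Its requirement is "≥1 ICD-10 diagnosis codes for UC and ≥1 prescription dispensing for a biologic (as identified by ATC codes) prior to and including". The window closes on the day of the first tofacitinib prescription, and the ADD threshold must also be met. It gives no look-back length for the biologic.

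Section 9.7.1.2.1 sends the analyst to the table: "The variables listed under 'Outcome: Compliance to recommended posology' in Table 3 will be described and tabulated". It offers no definition of its own.

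**The concern.** The outcome is meant to find UC patients at the higher ADD who had not first used an alternative. The written rule finds those who had. The two criteria are opposites, so a programmer who follows the definition column produces the count for the complementary group under a label that says otherwise.

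Table 3 gives three variables the role of compliance to recommended posology: ADD itself, and two patient-level threshold outcomes. This is one of those two, and the only one for UC. A reversed figure would therefore go straight into the assessment of whether prescribers follow the risk minimisation materials.

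**Working it through.** The protocol gives no expected value for this outcome, so there is no figure of its own to reproduce. The sample-size calculation in Section 9.5 (0.5 × 0.5 × 1.96² / 0.10² = 96.04, rounded up to 97) reproduces and does not depend on this point.

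**Step 1. Compare the biologic criterion wherever the protocol describes starting tofacitinib without a prior alternative.**

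| Place | Criterion |
|---|---|
| Section 9.3.1, this outcome | none |
| Table 3, this outcome, variable name | none |
| Table 3, this outcome, operational definition | at least 1, no window |
| Table 3, UC with a VTE risk factor | "0 prescription medication dispensings for a biologic (as identified by ATC codes) in the 12 months prior to and including the date of the index" |
| Table 3, age 65 and older at initiation | "0 prescription dispensings for a biologic (as identified by ATC codes) in the 12 months prior" |
| Table 3, CV risk factor | "0 prescription medication dispensings for a biologic (as identified by ATC code) in the 12 months prior to and including the date of the index" |
| Table 3, malignancy risk factor | same wording as the CV row |

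Four parallel rows use zero dispensings in 12 months. Only this row asks for at least one. Table 3 also shows the direction for patients who turn 65 on treatment: continuation with zero earlier biologics is labelled inappropriate, and continuation with at least one is labelled appropriate.

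**Step 2. Count who is selected.** Let N be the number of UC patients, h the number of them with ADD of at least 15 mg in any of the four intervals, and b the share of those h with a prior biologic.

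- Intended count: h·(1−b)
- Count as written: h·b
- Ratio, written to intended: b/(1−b)

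With the same look-back for both, the two groups do not overlap and together make up h. No patient who meets the written rule belongs to the named outcome. If the written rule is read with an unlimited look-back and the intended one with 12 months, the only overlap is patients whose last biologic was more than 12 months before index.

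**Step 3. Put in assumed numbers.** The documents give neither h nor b. For illustration take N = 100 and h = 20:

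| b | Intended, h(1−b)/N | As written, hb/N | Ratio |
|---|---|---|---|
| 20% | 16% | 4% | 0.25 |
| 50% | 10% | 10% | 1 |
| 60% | 8% | 12% | 1.5 |
| 80% | 4% | 16% | 4 |
| 90% | 2% | 18% | 9 |

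If the denominator is instead restricted to the h patients, the report shows b where 1−b is meant: 60% to 90% in place of 40% to 10% over the same range. The figures agree only at b = 50%, and even there they count different patients.

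**Step 4. Where it applies.** Sections 8 and 9.3.4 exclude Hungary and the Netherlands from every ADD outcome. That leaves Sweden and Germany, and both would use this row.

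**The case against.** The strongest reply is that this is a visible drafting slip in a provisional table. Section 9.3.2 calls the algorithms preliminary, leaves their refinement to the SAP, and provides for sponsor review before study start. The variable name on the same row shows the intent, so a careful programmer would query it. The SAP is not at hand and may already have corrected it.

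Part of this stands: the wrong result is conditional on the row being coded as written. But reversing a selection criterion is not the refinement of a code list, and Section 9.7 says major modifications of primary endpoint definitions belong in a protocol amendment. Detection after the fact may also be hard. Under Section 10.4 the German data owner runs the analysis and returns only aggregates.

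A second reply is that ADD is also reported in dose bands per interval, by indication group and by prior biologic use, so high-dose use without a biologic remains partly visible. That is true but not a substitute. The bands cut at above 15 mg, not at 15 mg or more; the protocol does not say that the strata are crossed; and interval-by-interval tables do not give a patient-level proportion over any of four intervals. The UC outcome with VTE risk factors covers only a subset and uses a different cut-off.

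A third reply is that the missing look-back has a default: Table 3 defines prior use of any biologic over 12 months, and Section 9.2.4 requires 12 months of history. That is fair. The missing window is a minor point beside the reversed criterion.

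**Conclusion.** The concern holds. The protocol contradicts itself within one Table 3 row, and the outcome name, Section 9.3.1 and four parallel rows all show that zero biologic dispensings is meant. Followed literally, the definition reports the complementary group among UC patients with ADD of at least 15 mg, in both countries where the outcome is assessed.

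It is the biologic criterion that is inverted. Over all UC patients, the reported proportion is h·b/N in place of h·(1−b)/N, which is not simply one minus the intended value. The factor of 1.5 to 9 rests on an assumed b of 60% to 90%; if b is below 50%, the error runs the other way. The contradiction itself rests on no assumption. It concerns variable coding only and implies no view on dosing.

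**What to change.** In the Table 3 row for UC with ADD of at least 15 mg, replace the requirement of at least one biologic dispensing with zero biologic dispensings in the 12 months up to and including the index date, matching the row for UC with a VTE risk factor. Leave the outcome name and Section 9.3.1 as they are, and carry the same definition into the SAP and the programming specifications sent to the Swedish and German analysis teams.

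The cost is one line of text in a protocol amendment. No new data are needed, and no sample size or timeline changes.

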- Compliance to patient screening and laboratory monitoring prior to and during tofacitinib treatment, as measured by:h
  - The proportion of patients with evidence of having received the following recommended screenings *prior to* initiation of tofacitinib:
    - Creatinine (serum or urine) laboratory testing;
    - TB screening;
    - Viral hepatitis B and C screening;
    - ALC laboratory testing;
    - ANC laboratory testing;
    - Haemoglobin laboratory testing; and

<sup>g Hungary will not have a VTE Reporting Period 1. Hungary will also not have a VTE Reporting Period 2 for PsA and UC.

<sup>h This outcome (and all sub-outcomes) will *not* be assessed in Sweden because the Swedish national health registers do not capture the laboratory tests of interest. In GKV claims, it may not be possible to differentiate an ALC laboratory test from an ANC laboratory test, or an ALT laboratory test from an AST laboratory test. In the PHARMO Database Network, TB screening and viral hepatitis B and C testing are not captured.

- ALT and/or AST laboratory testing (i.e., liver function testing);
- For patients with 6 and 12 months of tofacitinib therapy, the proportion of patients with evidence of having received the following recommended monitoring *after* initiation of tofacitinib in the respective periods:
  - TB screening;
  - Viral hepatitis B and C screening;
  - ALC laboratory testing;
  - ANC laboratory testing;
  - Haemoglobin laboratory testing;
  - ALT and/or AST laboratory testing; and
  - Lipid panel (i.e., total cholesterol, high-density lipoprotein [HDL], lowdensity lipoprotein [LDL], and triglycerides [TG]) laboratory testing;
- Compliance to recommendations to limitations for use, including
  - Use in patients with VTE risk factors, as measured by:e
    - The proportion of patients with evidence of  $\geq 1$  VTE risk factors *prior to* initiation of tofacitinib, reported overall and by approved indication;
    - The number of VTE risk factors identified *prior to* initiation of tofacitinib, reported overall and by approved indication;
    - The proportion of patients with UC who have: ≥1 VTE risk factor identified *prior to* tofacitinib initiation; no use of an alternative therapy (i.e., biologic) *prior to* tofacitinib initiation; and an ADD >10 mg in Weeks 16-23, Weeks 24-31, Weeks 32-39; and Weeks 40-47 of follow-up;f

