- In the 30 days prior to and including the day of tofacitinib initiation;
- In the 31 to 60 days prior to tofacitinib initiation;
- In the 61 to 90 days prior to tofacitinib initiation;
- In the 91 to 180 days prior to tofacitinib initiation;

For patients with 6 months of tofacitinib therapy (duration of tofacitinib therapy defined in Section 9.3.3):

- In the 60 days after and including the day of tofacitinib initiation;
- In the 61 to 120 days after tofacitinib initiation; and
- In the 121 to 180 days after tofacitinib initiation.

For patients with 12 months of tofacitinib therapy (duration of tofacitinib therapy defined in Section 9.3.3):

- In the 181 to 240 days after tofacitinib initiation;
- In the 241 to 300 days after tofacitinib initiation; and
- In the 301 to 360 days after tofacitinib initiation.

For analyses, 1 month will be defined as 30 days and 1 year will be defined as 360 days.

Timeframes for the baseline period are mutually exclusive. For patients with multiple procedure and/or diagnosis codes during the baseline period, the procedure or diagnosis code occurring closest to the index tofacitinib prescription dispensing will be selected.

<sup>u This outcome (and all sub-outcomes) will *not* be assessed in Sweden because the Swedish national health registers do not capture the laboratory tests of interest. In GKV claims, it may not be possible to differentiate an ALC laboratory test from an ANC laboratory test, or an ALT laboratory test from an AST laboratory test. In the PHARMO Database Network, TB screening and viral hepatitis B and C testing are not captured.

Variable	Role	Operational definition		
Creatinine (serum or urine) laboratory testing	Outcome: Screening	Defined as $\geq 1$ procedure code or $\geq 1$ ICD- 10 diagnosis code for a creatinine (serum or urine) laboratory test.		
TB screening	Outcome: Screening	Defined as $\geq 1$ procedure code or $\geq 1$ ICD-		
	Outcome: Monitoring	10 diagnosis code for TB (active and latent) screening.		
Viral hepatitis B and C	Outcome: Screening	Defined as $\geq 1$ procedure code or $\geq 1$ ICD-		
screening	Outcome: Monitoring	and C screening.		
Absolute lymphocyte	Outcome: Screening	Defined as $\geq 1$ procedure code or $\geq 1$ ICD-		
count (ALC) laboratory testing	Outcome: Monitoring	10 diagnosis code for ALC laboratory testing.		
Absolute neutrophil count	Outcome: Screening	Defined as $\geq 1$ procedure code or $\geq 1$ ICD-		

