#### 9.3.3. Duration of tofacitinib therapy

Duration of tofacitinib therapy will be defined as the time from the date of the index tofacitinib dispensing to the date of discontinuation of tofacitinib. The operational definitions for duration of tofacitinib therapy will be further elaborated in the SAP and made specific to each database. For example, for NHIFA, the Hungarian administrative claims database, the following proxy will be used to estimate duration: time between two prescription dispensings of tofacitinib, allowing for a grace period of a pre-determined length (e.g., 90 days) before being considered to have discontinued tofacitinib. The length of the grace period will be determined during development of the SAP.

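### Monitoring in four of the six post-initiation windows is counted only in patients who stay on tofacitinib to day 180 or day 360, so it does not describe monitoring among all patients treated through those windows

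*Protocol*

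**What the plan says.** The second primary objective (Protocol Section 8) includes compliance to laboratory monitoring during tofacitinib treatment and does not limit this to persistent users. Section 9.3.1 defines the corresponding primary outcome as "For patients with 6 and 12 months of tofacitinib therapy, the proportion of patients with evidence of having received the following recommended monitoring" in the respective periods.

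Table 3 in Section 9.3.2 gives the timeframes. Under "For patients with 6 months of tofacitinib therapy" it lists three windows. The first is "In the 60 days after and including the day of tofacitinib initiation"; the others are days 61-120 and 121-180. Under "For patients with 12 months of tofacitinib therapy (duration of tofacitinib therapy defined in Section 9.3.3" it lists days 181-240, 241-300 and 301-360. The same section fixes the calendar: "1 month will be defined as 30 days and 1 year will be defined as 360 days".

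Section 9.3.3 defines duration as "the time from the date of the index tofacitinib dispensing to the date of discontinuation of tofacitinib". This is achieved duration of therapy, not length of available records, and its database-specific rules are left to the SAP. Section 9.7.1.2.2 adds only that the Table 3 variables will be tabulated.

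Section 9.5 mentions the six-month requirement as a reason for smaller numbers and varying precision. Section 9.9 does not discuss it. The comment under Section 7 of the ENCePP checklist (Annex 2) says that selection bias is not a concern, because the study is descriptive and has no control group.

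**The concern.** Whether a patient counts in the day 0-60 window is decided by what happens up to day 180. Someone treated for 100 days without a laboratory test had a complete first window on drug, yet appears in no monitoring proportion. The same happens in the second half of the year to a patient who stops at, say, day 260: the day 181-240 window was completed but is not counted.

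Stopping can plausibly be linked to monitoring in two opposite ways. An abnormal result may lead to stopping, which makes stoppers better monitored than persisters. Loss of contact with care may lead both to stopping and to missed tests, which makes them worse monitored. In either case the proportion among completers differs from the proportion among everyone treated through the window. The lack of a control group gives no protection, because a single-group proportion is also biased when its denominator is selected on a later event related to the outcome. At stake is a primary compliance measure of a study meant to judge whether the risk minimisation materials work.

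**Working it through.** **1. Which windows are affected.** With 1 month = 30 days, 6 months = 6 × 30 = 180 days and 12 months = 12 × 30 = 360 days. The therapy required by Table 3 compares with the therapy needed to complete each window as follows:

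| Window (days) | Therapy required | End of window | Excess requirement |
|---|---|---|---|
| 0-60 | 180 | 60 | 120 days |
| 61-120 | 180 | 120 | 60 days |
| 121-180 | 180 | 180 | none |
| 181-240 | 360 | 240 | 120 days |
| 241-300 | 360 | 300 | 60 days |
| 301-360 | 360 | 360 | none |

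Four windows look ahead. Two already require therapy only to their own end.

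**2. Whether the data force the restriction.** Inclusion criterion 3 (Section 9.2.4) requires 12 months of available history after the index dispensing for every patient. Early stoppers therefore have records as long as those of completers. The 8-week dose intervals in Section 9.3.4 carry no 6- or 12-month completion condition.

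**3. The plan's own figure.** Section 9.5: n = P(1-P)z²/e² = 0.50 × 0.50 × 1.96² / 0.10² = 96.04, so 97, rounded up to 100 per indication and country. This reproduces. The restriction's effect on precision is disclosed there in general terms. With 100 initiators and an assumed 80%, 70% or 60% on therapy at day 180, the 95% CI width at P = 0.5 is 2 × 1.96 × √(0.25/m). For m = 80, 70 and 60 this gives 21.9, 23.4 and 25.3 points, against 19.6 for m = 100. The formula describes precision only and says nothing about who is left in the denominator.

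**4. Illustration for days 0-60.** The documents give no persistence or monitoring rates, so all inputs here are assumptions. Let S60 and S180 be the shares on therapy at days 60 and 180. Persisters are monitored at 80%, and patients who stop between days 60 and 180 are monitored at 50% or 90% (m_stop).

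- Dropped share of patients with a full first window = (S60 - S180)/S60
- Rate in all treated through day 60 = [S180 × 0.80 + (S60 - S180) × m_stop]/S60

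| S60 / S180 | Dropped | Rate, stoppers 50% | Rate, stoppers 90% |
|---|---|---|---|
| 0.95 / 0.80 | 0.15/0.95 = 15.8% | (0.640 + 0.075)/0.95 = 75.3% | (0.640 + 0.135)/0.95 = 81.6% |
| 0.90 / 0.70 | 0.20/0.90 = 22.2% | (0.560 + 0.100)/0.90 = 73.3% | (0.560 + 0.180)/0.90 = 82.2% |
| 0.90 / 0.60 | 0.30/0.90 = 33.3% | (0.480 + 0.150)/0.90 = 70.0% | (0.480 + 0.270)/0.90 = 83.3% |

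The plan would report 80% in every row. The gap is 5 to 10 points too high or about 2 to 3 points too low.

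**The case against.** The strongest defence is that the estimand is declared. Section 9.3.1 names the 6- and 12-month groups, Section 9.5 admits the smaller numbers, and no comparative analysis is planned. One fixed cohort followed over three consecutive windows is a legitimate descriptive quantity, and it allows windows to be compared without a changing denominator. That stands as a reason to keep the display. It does not make it sufficient, because the objective is wider and no other tabulation covers the patients left out.

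Four further points limit the finding:

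- A reader might infer that all six windows are affected. The table in step 1 shows that days 121-180 and 301-360 are not.
- A reader might infer that compliance will be overstated, or that every dropped patient had missed a test that was due. The documents support neither. The direction is open, and the protocol states no testing interval for the individual tests.
- The size rests on assumed rates and is worked only for days 0-60. Under the same reasoning no more are dropped at 61-120, and none at 121-180. Who counts as a stopper also depends on duration and grace-period rules that Section 9.3.3 leaves to the SAP.
- A denominator of patients on therapy through the end of the window still drops someone tested on day 30 who stops on day 45 because of the result. Some selection therefore remains after the change, which is why a second tabulation is needed.

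The reach is also limited. Pre-initiation screening carries no duration condition, Sweden does not assess this outcome, and the Dutch data lack tuberculosis and hepatitis testing.

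**Conclusion.** The point holds for four windows: days 0-60, 61-120, 181-240 and 241-300. Their denominators depend on persistence beyond the window, so the proportions do not describe monitoring during treatment among all patients treated through them. This is fixed in the protocol's outcome and variable definitions. It is not a detail left to the SAP, although the duration rules are. No stated number is wrong.

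Size and direction cannot be taken from the documents. The range of 16-33% dropped, with a reported 80% against 70-75% or 82-83%, shows only what the assumed persistence and monitoring rates would produce. The change is worth making because it reduces a selection in a primary outcome at little cost. It does not rest on a demonstrated error of known magnitude.

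**What to change.** 1. For each monitoring window, use as denominator all patients on therapy through the end of that window: day 60, 120, 180, 240, 300 or 360.
2. Add a sensitivity tabulation among patients on therapy at the start of each window, to cover those who stop within it.
3. Keep the 6- and 12-month completers as an additional fixed-cohort display.
4. State the remaining selection in Section 9.9, and correct the checklist comment that selection bias is of no concern.

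No new data are needed, because the duration variable of Section 9.3.3 is already planned. The cost is that denominators vary across windows, so each proportion must be shown with its own n, and comparisons across windows should be read from the fixed-cohort display. Sections 9.3.1 and 9.3.2 need matching wording. If the change counts as a major modification of a primary endpoint definition, Section 9.7 requires a protocol amendment.
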